### **Risks**

The tDCS protocol for this experiment was determined according to the best practices observed in previous research using tDCS stimulation [45]. Furthermore, tDCS is safe, has virtually no side effects, is technically easy to carry out, and is not uncomfortable to undergo [46,47]. Multiple studies have also reported that the administration of 4 ma tDCS has no more adverse effects than 2 ma tDCS [48]. No incidence of seizure has been recorded, although side effects could include headache, drowsiness, itching sensation, nausea, and, in rare cases, disorientation. In our experiences, the only observed and reported side-effect has been temporary redness post-stimulation where the sponge was placed, as well as the occasionally reported headache.

If the event were to result in lasting pain and hospitalization, then it would be reported as a 'Serious Adverse Event' and full details would be noted to the research ethics board as well as Health Canada. These events would be recorded on the worksheets being used to collect the rest of the data. We must stress, however, that after administering 4 mA tDCS to around 60 participants, for hundreds of tDCS sessions, we have never encountered any such event. Although we have safety protocols in place for any encountered adverse or severe adverse events, we believe such events will fail to occur in the present study.

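### The only written trigger for a serious adverse event requires lasting pain and hospitalisation together, so hospitalisation without lasting pain does not meet it

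*Protocol*

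**What the plan says.** The protocol's Risks section first describes what might happen to a participant: "side effects could include headache, drowsiness, itching sensation, nausea, and, in rare cases, disorientation". It adds that no seizure has been recorded, and that the team has itself seen only temporary redness under the sponge and an occasional headache.

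It then gives the reporting rule. The condition is "If the event were to result in lasting pain and hospitalization", and an event that meets it is classed as a serious adverse event. Once that condition is met, "full details would be noted to the research ethics board as well as Health Canada". On documentation it says: "These events would be recorded on the worksheets being used to collect the rest of the data".

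The section closes with a reassurance that begins "Although we have safety protocols in place for any encountered adverse or severe adverse events" and goes on to say that the team expects no such events in this study. No other section of the protocol defines a serious event or gives another trigger for notifying an outside body.

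**The concern.** The rule is stated, so the issue is what it says and not a detail left for another document. Read as written, it asks for two outcomes at once. Staff who apply it literally to a participant admitted to hospital without lasting pain would find the condition unmet. The same holds for lasting pain without admission, and for a grave outcome that involves neither.

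The rule also fits poorly with its own section, where most of the possible effects named are not pain. Disorientation matters most here, because the Sample section enrols people with mild to moderate Alzheimer's disease.

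At stake is whether the two oversight bodies are told of serious events in a study that includes the higher 4 mA intensity. The shift from *serious* to *severe* adds to the difficulty: the reader cannot tell whether one category of event is meant or two.

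**Working it through.** There is no figure to reproduce and no formula applies. The check is a logical reading of the rule, set beside the events named in the same section.

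**Step 1. Inputs, all from the Risks section.**
- Condition: lasting pain, joined by *and* to hospitalisation.
- Consequence: the event is classed as serious, and the ethics board and Health Canada receive full details.
- Other provision: safety protocols are said to exist, with no description of their content.

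**Step 2. Apply the condition to every combination.**

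| Lasting pain | Hospitalisation | Written condition met? |
|---|---|---|
| Yes | Yes | Yes |
| Yes | No | No |
| No | Yes | No |
| No | No | No |

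One combination of four meets the condition. If the two outcomes were alternatives, three of four would.

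**Step 3. Compare with the events the section names.**

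| Event named | Itself pain? | Would hospitalisation for it, with no lasting pain, meet the condition? |
|---|---|---|
| Headache | Yes | No; met only if the headache also counts as lasting |
| Drowsiness | No | No |
| Itching | No | No |
| Nausea | No | No |
| Disorientation | No | No |
| Seizure (mentioned as never recorded) | No | No |

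Four of the five listed side effects, and seizure, are not pain. For these the condition is met only if lasting pain happens to accompany the admission. The count describes how well the rule fits the listed events. It does not estimate how many events would be missed, and the protocol gives no rates from which to make such an estimate.

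**Step 4. Look for another route to reporting.** The worksheet sentence concerns recording and adds no trigger. The safety protocols are mentioned but not described, so nothing shown says that they widen the condition. The Planned Analyses section covers naming outcomes only.

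**Step 5. Check the terms.** The rule uses *serious*. The closing sentence uses *severe* and does not say whether the same events are meant.

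**The case against.** The best case on the other side has five parts.

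- **The sentence says *if*, not *only if*.** It commits the team to reporting one kind of event and does not exclude others. This stands. A reader might infer that a hospitalisation without lasting pain would go unreported, but the protocol does not say so. What can be said is that such an event does not meet the only trigger written.
- **The safety protocols may hold the working definition.** They may, and some pages were not available for review. This limits the conclusion but does not remove the need for the sentence to agree with them.
- **The passage is informal prose, and the authors may have meant examples of serious harm and not a two-part test.** This is plausible. The literal reading is still the plain one, and staff apply what is written, so the possibility is itself a reason to correct the sentence.
- **Calling the rule wrong needs an outside definition of a serious event.** The point does not depend on one. The mismatch is between the rule and the events named beside it, and the protocol itself treats hospitalisation as bearing on seriousness.
- **No such event has occurred in around 60 participants given 4 mA.** That reassurance comes after the narrow condition and appears to refer back to it, so it does not show that hospitalisation without lasting pain has been absent. The expectation of no events does not repair a reporting rule either.

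A further inference should also be resisted: that a planned conclusion about the relative safety of 4 mA, 2 mA and SHAM would rest on an undercount. No such conclusion is planned. The section on communication of results speaks of effectiveness, and the comparison of 4 mA with 2 mA in the Risks section cites earlier studies as background.

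**Conclusion.** The concern holds as a defect in the wording of a stated safety-reporting rule. The only written trigger requires both outcomes, is met by one of their four combinations, and does not cover hospitalisation without lasting pain. Two lesser faults go with it: *serious* and *severe* are used without distinction, and the safety protocols are cited without description.

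The conclusion assumes that the sentence is read literally and that no material outside the protocol text shown supplies a wider definition. If the safety protocols do supply one, the fault becomes an inconsistency between two documents, and it still needs correcting.

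The effect on the number of reports cannot be quantified from the protocol. Sample size, power, endpoints and the primary analysis are not affected. The change should be made because it bears on participant safety oversight and costs very little.

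**What to change.** In the Risks section:

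1. Reword the trigger so that lasting pain and hospitalisation are alternatives, with hospitalisation alone sufficient.
2. For any remaining criteria, refer to the serious-event definition of the two bodies the protocol already names, the research ethics board and Health Canada.
3. Use one term throughout. If *severe* is meant to differ from *serious*, say how.
4. Reconcile the sentence with the safety protocols, and either cite them or state briefly what they require.

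The cost is essentially one sentence in the protocol and possibly a few more event reports. No intensity, visit, endpoint, analysis or sample size changes.

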### **Confidentiality**

A research study file as well as medical records identifying participants will be maintained within [name] lab. Names and identifying information will be replaced with a code, and the

information will be kept on file for 10 years after the end of the study. Data collected from participants' who withdraw from the study will also be kept, unless participants withdraw consent for its use.

### **Communication and Publication of Research Results**

The found results may be presented at research conferences and written up in a manuscript submitted for a publication in a respected science journal. The data will never be used for commercial goals and all participant information will remain confidential. Individual's participant data will be presented using a code (e.g., Participant 1), which ensures no reader of the data could identify the participant. The results found can also be used to back-up further studies involving 4 mA tDCS because we will be able to present formal data demonstrating its effectiveness compared to other intensities of stimulation (SHAM, 2mA) in people with Alzheimer's Disease.

